3.2 Trial Treatments

The dose of centanafadine SR that participants receive is 400 mg TDD (200 mg BID) approximately 4 to 6 hours apart for seven weeks.

The IMP dose may be considered for a one-time dose decrease based on tolerability and/or adverse events (AEs). A one-time dose decrease to 200mg TDD, based on the clinical judgement of the investigator, may be considered. The subject would remain on the decreased dose (200mg TDD) for the remainder of trial participation. If tolerability / AE does not resolve, post IMP dose-reduction, the subject should be considered for trial discontinuation, based on investigator judgement.

3.3 Trial Population

The study population includes 50 cigarette smoking adults. Smokers between 21 and 65 years of age (inclusive), 18 to 40 kg/m² (inclusive) of body mass index(BMI), with no restriction on gender, race and ethnicities, or social-economic status, and have smoked an average of at least 10 commercially available cigarettes per day for the last 12 months will be screened. Subjects who have an expired air carbon monoxide (CO) reading of at least 10 ppm at screening, express a desire to quit smoking within the next 30 days, and own a smart phone with text message and data capabilities compatible with necessary surveys will be eligible for inclusion.

4 Sample Size

This is a single-arm trial to assess the effect of centanafadine for a four-week continuous smoking abstinence rate during Week 4 to Week 7.

[Table 4-1](#) shows the 90% confidence interval for 50 subjects when the four-week continuous smoking abstinence rate is 0.3, 0.4, 0.45 and 0.5.¹

Table 4-1 90% Confidence Interval for Sample Size of 50 Subjects						
Confidence Level	Sample Size	Actual Width	Proportion	Lower Limit	Upper Limit	
0.9	50	0.22885	0.3	0.19488	0.42373	
0.9	50	0.24299	0.4	0.28313	0.52612	
0.9	50	0.24639	0.45	0.32912	0.5755	
0.9	50	0.24751	0.5	0.37625	0.62375	

Lower limit and upper limit are 90% confidence interval of the proportion given the sample size and proportion of four-week continuous smoking abstinence.

Protocol 405-201-00055 Statistical Analysis Plan

5 Statistical Analysis Datasets

5.1 Enrolled Analysis Set

Enrolled Analysis Set includes all subjects who sign an informed consent form (ICF) for the trial and are assigned to treatment at the baseline visit.

5.2 Safety Analysis Set (SAS)

Safety Analysis Set includes all subjects who are administered at least one dose of IMP, regardless of any protocol violation.

5.3 Full Analysis Set (FAS)

Full Analysis Set includes all subjects who are administered at least one dose of IMP.

5.4 Trial Visit Window

The actual assessment date is mapped into the trial week based on [Table 5.4-1](#). Trial days are derived from the formula: Trial Day = Date of assessment - Date of 1st IMP + 1. Based on the number of trial days, subjects are mapped to the corresponding trial week. In addition, only last observations within the same mapped weeks are reported in the summary tables by trial week.

Table 5.4-1 Mapped Trial Week Windows for Efficacy Analysis	
Mapped Week	Mapped Trial Day Range^{a,b}
Week 1	Day 1 - Day 7
Week 2	Day 8 - Day 14
Week 3	Day 15 - Day 21
Week 4	Day 22 - Day 28
Week 5	Day 29 - Day 35
Week 6	Day 36 - Day 42
Week 7	Day 43 - Day 49

^a Relative days to the first day of IMP.

^b Evaluations occurring more than three days after the last dosing date will be excluded from the analyses.

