4.9.3 All other visit Windows

Participants may attend sessions up to three calendar days pre or post the scheduled visit.

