5.2 DOSING REGIMEN

Centanafadine SR will be administered orally at a 400 mg TDD (200 mg BID) approximately 4 to 6 hours apart for a total of seven weeks. Doses of centanafadine SR can be taken without regard to meals and should be taken at approximately the same time each day, with the first dose taken in the morning. The second dose should be taken 4 to 6 hours after the first dose. If a subject forgets to take their second dose, they can take it up to 7 hours after their first dose; if they remember after 7 hours, they should skip the dose and resume dosing the next day.

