3.1 Type/Design of Trial

This single-group, small-scale, open-label, phase 2 study evaluates centanafadine as a potential smoking cessation treatment. Participants enrolled in the study will be given centanafadine SR at a dose of 400 mg total daily dose (TDD) (200 mg twice daily [BID]) approximately 4 to 6 hours apart for seven weeks. The study consists of a 28-day screening period, a baseline visit, a 7-week treatment period, and a 7-day safety follow-up period. Participants visit the study center a total of 6 times, including a screening visit (V1), baseline visit (V2), a visit one week (+3 days) after starting the study drug (Week 1 visit V3), three weeks (± 3 days) after starting the study drug (Week 3 visit V4), five weeks (± 3 days) after starting the study drug (Week 5 visit V5), and seven weeks (± 3 days) after starting the study drug (Week 7 visit V6). All participants are requested to participate in a 7-day safety follow up period, which will consist of telephone contact seven days (+2 days) after the last dose of investigational medicinal product (IMP).

A schematic of the trial design for this study is provided in [Figure 3.1-1](#).

[figure not shown]

Figure 3.1-1 Trial Design Schematic

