8.3.6 Abstinence Rate by Week

Abstinence rate calculation:

- If subject has exhaled CO level of less than 5 ppm using the Vitalograph BreathCO monitor and there is no smoking in the self-report, then set it as abstinence.
 - Missing value check:
 - For CO value, value can be missing.
 - For self-report value, only one missing in every visit week (7 days) is allowed.

Protocol 405-201-00055 Statistical Analysis Plan

- All the others will be set as non-abstinent.
 - There are two or more missing in self-report every visit week (7 days)
 - Lost to follow-up/Early termination
 - Subjects with adequate data that they were smoking

A descriptive statistic will be provided with 90% binomial confidence intervals by week.

For all binomial confidence intervals, it is based on normal approximation. If the number of abstinent or the number of non-abstinent ≤ 5 , we will use the exact method.

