CT-3.4 Medical History (Enrolled Analysis Set)

CT-4.1 Concomitant Medications: Medications Taken Prior to Start of Study Therapy (Enrolled Analysis Set)

CT-4.2 Concomitant Medications: Medications Taken During Study (Enrolled Analysis Set)

CT-5.1.1.1 Smoking Continuous Abstinence Rate During Week 4-7 (Full Analysis Set)

CT-5.1.1.2 Smoking Continuous Abstinence Rate During Week 4-7 - Sensitivity Analysis I (Full Analysis Set)

CT-5.1.1.3 Smoking Continuous Abstinence Rate During Week 4-7 - Sensitivity Analysis II (Full Analysis Set)

CT-5.1.1.4 Smoking Continuous Abstinence Rate During Week 4-7 - Sensitivity Analysis III (Full Analysis Set)

CT-5.1.1.5 Smoking Continuous Abstinence Rate During Week 4-7-Using Only Exhaled Carbon Monoxide Level (Full Analysis Set)

[figure not shown]
CT-5.1.1.6 Smoking Continuous Abstinence Rate During Week 4-7 - Using Only Self-report (Full Analysis Set)

CT-5.1.2 Summary of Non-smoking Rate from Self-report and CO Level by Week (Full Analysis Set)

Protocol 405-201-00055 Statistical Analysis Plan

[figure not shown]
CT-5.1.3 Summary of Non-smoking Rate from Self-report by Week (Full Analysis Set)

CCI

Protocol 405-201-00055 Statistical Analysis Plan

CCI

CT-6.1.1 Expired Air CO breath Test Result (Full Analysis Set)

CT-6.1.2 Summary of Subjects with CO Level Greater Than or Equal to 5 PPM (Full Analysis Set)

CT-6.2 Summary of Change from Baseline in Average Number of Cigarettes Smoked Per Day by Week (Full Analysis Set)

CT-7.1 Extent of Exposure (Safety Analysis Set)

CT-7.2 Number and Percentage of Subjects Receiving Study Medication and Mean and Range of Average Daily Dose (Safety Analysis Set)

CT-8.1 Incidence of Adverse Events (All Causalities) (Safety Analysis Set)

Protocol 405-201-00055 Statistical Analysis Plan

CT-8.2.1 Incidence of Treatment-emergent Adverse Events by System Organ Class and MedDRA Preferred Term (Safety Analysis Set)

CT-8.2.2 Incidence of Treatment-emergent Adverse Events by System Organ Class, MedDRA Preferred Term and Severity (Safety Analysis Set)

CT-8.2.2.1 Incidence of Treatment-emergent Adverse Events Greater Than or Equal to 5% by System Organ Class and MedDRA Preferred Term (Safety Analysis Set)

CT-8.2.2.2 Incidence of non-Serious Treatment-emergent Adverse Events Greater Than or Equal to 5% by System Organ Class and MedDRA Preferred Term (Safety Analysis Set)

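### SAP Table 5.4-1 stops at Day 49, so a V6 held late but within its window has no mapped week, and its CO reading can drop out of the Week 7 abstinence rate in SAP 8.3.6

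*SAP*

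**What the plan says.** SAP 5.4 counts days from the first dose: "Trial days are derived from the formula: Trial Day = Date of assessment - Date of 1st IMP + 1". It then states "Based on the number of trial days, subjects are mapped to the corresponding trial week". Table 5.4-1, which is headed as applying to efficacy analysis, has seven rows of seven days. The last is Week 7, Days 43 to 49, and nothing follows it. Footnote b adds a cut-off: "Evaluations occurring more than three days after the last dosing date will be excluded from the analyses".

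SAP 3.1 places the last visit at "seven weeks (± 3 days) after starting the study drug (Week 7 visit V6"), and Protocol 4.9.3 gives the same tolerance: "Participants may attend sessions up to three calendar days pre or post the scheduled visit".

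SAP 8.3.6 defines a weekly abstinence rate from CO and daily self-report. On missing CO it says "For CO value, value can be missing"; on missing self-report it allows one day per week. It also classes as non-abstinent any subject for whom there is adequate evidence of smoking. SAP 17 lists the output as CT-5.1.2, "Summary of Non-smoking Rate from Self-report and CO Level by Week".

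For the primary endpoint (SAP 8.1.1) and the CO-only rate (SAP 8.3.7), CO is read at the scheduled Week 5 and Week 7. A missing Week 7 CO makes the subject non-abstinent in 8.1.1; a missing value at either time does so in 8.3.7.

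**The concern.** The visit window and the analysis window do not fit together. A participant can attend V6 exactly as the protocol permits and still provide a CO reading that the mapping table cannot place. Footnote b does not close the gap: it says which readings to exclude, but gives no week to those that survive.

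The exposed output is the weekly rate in 8.3.6. V6 is the only scheduled CO test after V5. If V6 falls after Day 49, Week 7 normally holds no CO at all. Because a missing CO is tolerated there, a late reading of 5 ppm or more can have no effect, and a subject with a clean diary counts as abstinent. The error runs in the favourable direction, in the table meant to combine self-report with biochemical evidence.

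If the same mapping were carried into 8.1.1 or 8.3.7, the error would run the other way: a late V6 would become a missing Week 7 CO and an abstainer would be scored as non-abstinent. SAP 5.4 exempts neither analysis in words.

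**Working it through.** **Inputs.** Day formula and week table: SAP 5.4. V6 at seven weeks, plus or minus three days: SAP 3.1, Protocol 4.9.3 and 6.6.6. Sample size 50: SAP 3.3 and 4. Dosing "approximately 4 to 6 hours apart for a total of seven weeks": Protocol 5.2.

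**Reproducing the table.** Week k = Day 7(k − 1) + 1 to Day 7k. For k = 7 this gives Days 43 to 49, and the rule returns all seven rows of Table 5.4-1.

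**V6 due day.** Protocol 6.6.3 heads V3 as one week on treatment and places it six days after starting, which is Day 7. By that convention seven weeks is Day 49. Adding 49 days to the date of first dose would give Day 50.

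| V6 due | Permitted days | Mapped to Week 7 | No week |
|---|---|---|---|
| Day 49 | 46–52 | 46–49 (4 of 7) | 50–52 (3 of 7) |
| Day 50 | 47–53 | 47–49 (3 of 7) | 50–53 (4 of 7) |

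**Footnote b.** The cut-off is last dose day + 3. The last dose day is an assumption.

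| Last dose | Last day kept | In-window V6 excluded, due Day 49 | In-window V6 excluded, due Day 50 |
|---|---|---|---|
| Day 48 | 51 | 52 | 52, 53 |
| Day 49 | 52 | none | 53 |
| Day 50 | 53 | none | none |

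With the last dose on Day 49, Days 50 to 52 are kept by the footnote but have no week in the table.

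**Size in 8.3.6.** One subject is 1/50 = 2.0 percentage points. As illustration only, 1 to 5 affected subjects would add 2 to 10 points. For scale, the normal-approximation 90% half-width at 50% is 1.645 × √(0.25/50) = 0.116, or 11.6 points.

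**V5, if the mapping were applied.** Days 36 to 38 (due Day 35) or 36 to 39 (due Day 36) map to Week 6. Only 8.3.7, which needs both readings, would fail an abstainer on that ground alone.

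**Separate check: when the diary stops.** Protocol 6.7.2 and the Schedule of Events end the smoking-status messages at V6. Protocol 6.5.16.10 runs them to End of Study, which the Explanation of Terms sets at the safety follow-up or early termination. If they stop at V6 and the V6-day message is answered, missing days in Days 43 to 49 = 49 − V6 day:

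- V6 on Day 46: 3 missing
- V6 on Day 47: 2 missing
- V6 on Day 48: 1 missing

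Two or more missing days fail the rule in 8.1.1. That is 2 of 7 permitted V6 days (due Day 49) or 1 of 7 (due Day 50). If the V6-day message is not answered, add one missing day: 3 of 7 or 2 of 7.

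**The case against.** A reader might infer that the primary endpoint loses CO data. The documents do not support that. The Protocol Synopsis defines the primary endpoint by CO at Visit 5 and Visit 6; SAP 3.1 labels those visits Week 5 and Week 7; SAP 8.1.1 speaks of scheduled weeks; and SAP 9.3 uses the same visit labels for laboratory tests. On that reading the mapping costs the primary nothing. SAP 8.3.7 uses the same wording, but its support is indirect, since the Synopsis speaks only of the primary.

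A reader might also infer that the effect on 8.3.6 is certain. It is not. An analyst could use the line about adequate evidence of smoking to count a late reading of 5 ppm or more. But that line does not assign the reading to a week, so using it would be an undocumented programming choice.

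Footnote b's three-day allowance matches the upper side of the V6 window, which suggests that late V6 readings were meant to be kept. V5 also dispenses enough drug to last until V6; if dosing runs up to V6, the footnote excludes no in-window V6. Both points stand. They make this a wording gap rather than a plan to discard data, but the table still gives no week.

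Materiality is limited. Harm needs a late V6, a CO of 5 ppm or more and a clean diary in the same subject, and it reaches one week of a descriptive table. On the nominal reading the same subject is non-abstinent in the primary, and CT-6.1.2 separately summarises readings of 5 ppm or more.

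The messaging conflict is a different matter: it concerns early V6 visits, not late ones, and should not add weight to the mapping point.

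**Conclusion.** The gap is real and small. Three of the seven permitted V6 days have no mapped week if V6 is due on Day 49, the better-supported reading; four of seven if it is due on Day 50. With Table 5.4-1 applied as written, each clean-diary subject with a late V6 CO of 5 ppm or more raises the 8.3.6 Week 7 rate by 2 points, assuming all 50 planned subjects are in the denominator. The documents give no attendance pattern, so the total is unknown.

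The expected CO loss in the primary is zero under the nominal-visit reading. Only if 5.4 were applied there would each late-V6 abstainer lower the rate by 2 points. A loss of that kind would show against Sensitivity Analysis I and the self-report-only rate in 8.3.8.

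The messaging conflict can reach the primary even on the nominal reading, but only if messages stop at V6. An abstainer attending on Day 46 or 47 would then be scored as non-abstinent. The self-report-only rate would not reveal this, because it uses the same one-missing rule. Its size is also unknown; if messages run to End of Study, no such loss arises.

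**What to change.** - **SAP 5.4:** assign any V6 CO within its permitted window to Week 7, state whether V6 is due on Day 49 or Day 50, and check that footnote b cannot exclude an in-window V6.
- **SAP 8.1.1 and 8.3.7:** confirm that the scheduled Week 5 and Week 7 readings are those of nominal V5 and V6.
- **Diary:** keep Days 22 to 49. V3 to V5 can keep their calendar mapping in 8.3.6, because it pairs each CO with the diary of the same week.
- **Messaging:** reconcile Protocol 6.7.2 and the Schedule of Events with 6.5.16.10 so that smoking-status messages cover Day 49, or count missing diary days only up to V6.

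The cost is a few sentences in the SAP, a footnote check and one line in the protocol, with no extra visits or data. The one small downside is that a CO from Days 50 to 52 (or 53) is paired with the diary for Days 43 to 49 and could reflect smoking just after that week. These changes should be settled before database lock.

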11.3.1 Smoking Abstinence

Complete abstinence from combustible cigarette use at each time point will be defined by a self-report of no cigarette smoking (not even a puff) since the prior session, confirmed by an expired air CO reading of less than 5 ppm. The primary outcome will be four-week continuous smoking abstinence during weeks 4-7. An intent-to-treat approach will be taken in which any participants lost to follow-up after receiving the investigational product, or who have smoked during weeks 4-7 will be counted as non-abstinent.

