8.1.1 Primary Efficacy Analyses

The primary endpoint with the treatment of centanafadine is the four-week continuous abstinence rate of subjects during Week 4 to Week 7. A participant is considered abstinent from combustible cigarettes if he or she self-reports tobacco abstinence (no cigarette smoking, not even a puff) assessed by responses to daily messages throughout the period and has an exhaled CO level of less than 5 ppm using the Vitalograph Breath CO monitor in the office at scheduled Week 5 and Week 7. An intent-to-treat approach is

Protocol 405-201-00055 Statistical Analysis Plan

taken in which any participants lost to follow-up / early termination after receiving the IMP, or who have smoked during Week 4 to Week 7 will be counted as non-abstinent.

Primary endpoint calculation:

- Set it as four-week continuous abstinence:
 - If there is no smoking in the self-report.
 - And if subject has exhaled CO level of less than 5 ppm using the Vitalograph BreathCO monitor in the office at scheduled Week 5 or Week 7 value is missing.
 - And if subject has exhaled level of less than 5 ppm using the Vitalograph BreathCO monitor in the office at scheduled Week 7.
 - Missing value check:
 - For CO value, only one missing value is allowed, and Week 7 value cannot be missing.
 - For self-report value, only one missing in each visit Week (7 days) is allowed. The missing value is checked per each week.
- All the others will be set as non-abstinent.
 - Week 7 CO value is missing
 - Two or more missing in self-report in each visit week (7 days)
 - Lost to follow-up/Early termination
 - Subjects with actual data that they were smoking. (CO value \geq 5 ppm or any smoking record in self-report.)

A descriptive statistic will be provided for the continuous smoking abstinence rate during Week 4 to Week 7 with 90% binomial confidence intervals. For all binomial confidence intervals, it is based on normal approximation. If the number of abstinent or the number of non-abstinent ≤ 5 , we will use the exact method.

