8.1.2 Sensitivity Analysis I

Missing value is allowed. No need to check missing value. All the missing values during the treatment period will be considered as no-smoking.

Sensitivity analysis I endpoint calculation:

- Only subjects with adequate data that they were smoking during Week 4 to Week 7 are set as non-abstinent.
 - There is smoking in the self-report
 - Or subject has exhaled CO level of greater or equal to 5 ppm using the Vitalograph Breath CO monitor in the office at scheduled Week 5 and Week 7.

Protocol 405-201-00055 Statistical Analysis Plan

- Subjects lost to follow-up/Early termination will be set as non-abstinent.
- All other subjects having missing value in CO value and self-report will be set as abstinent.

A descriptive statistic will be provided with 90% binomial confidence intervals.

For all binomial confidence intervals, it is based on normal approximation. If the number of abstinent or the number of non-abstinent ≤ 5 , we will use the exact method.

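### SAP Table 5.4-1 footnote b drops diary and CO records once dosing has stopped for over three days, which does not fit the stated intent-to-treat abstinence endpoint

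*SAP*

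**What the plan says.** SAP 5.4 maps assessments to trial weeks in a table titled "Mapped Trial Week Windows for Efficacy Analysis". Its footnote b reads: "Evaluations occurring more than three days after the last dosing date will be excluded from the analyses". By its title the table covers efficacy data, so the footnote reaches the daily smoking reports and CO readings behind the abstinence endpoints.

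The population and the endpoint are defined without reference to staying on drug:

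- SAP 5.3: "Full Analysis Set includes all subjects who are administered at least one dose of IMP".
- Protocol 11.3.1: "An intent-to-treat approach will be taken in which any participants lost to follow-up after receiving the investigational product", or who smoked in Weeks 4-7, is counted as non-abstinent.
- SAP 8.1.1 repeats this for "any participants lost to follow-up / early termination after receiving the IMP" and for those "who have smoked during Week 4 to Week 7 will be counted as non-abstinent".

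SAP 8.1.1 also makes a participant non-abstinent if "Week 7 CO value is missing", or if two or more self-reports are missing in a week. Sensitivity II and III relax the diary allowance to two and three missing per week but still require the Week 7 CO. Sensitivity I goes the other way: "All the missing values during the treatment period will be considered as no-smoking". Under it, everyone without recorded smoking is abstinent unless lost to follow-up or terminated early.

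**The concern.** Footnote b is an on-treatment rule placed under an endpoint that the plan describes as intent-to-treat, and the SAP does not say which prevails. The records it removes can exist. Smoking-status messages run through End of Study (protocol 6.5.16.10), and CO is measured at every visit (protocol 6.5.10).

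Once removed, the records look like missing data, and the four abstinence analyses treat missing data in opposite ways. The primary analysis and Sensitivity II and III penalise the gap, while Sensitivity I reads it as no smoking. One footnote can therefore lower the primary rate and raise Sensitivity I, in both cases by discarding outcomes that were observed.

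**Working it through.** **The plan's own figure.** SAP Table 4-1 gives a 90% interval of 0.37625 to 0.62375 for 50 participants at a rate of 0.50. The exact (Clopper-Pearson) method returns 0.3762 to 0.6238, and all four rows reproduce. The normal approximation that SAP 8.1.1 specifies for the analysis gives 0.3837 to 0.6163. The benchmark arithmetic below uses the SAP 8.1.1 method.

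**Which records go.** A record on day d is dropped if d > last dose day + 3.

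- Last dose Day 40: Day 44 onward is dropped. Week 7 is Days 43-49, so 6 of its 7 diaries go, as does a CO reading on Day 49.
- Last dose Day 45, V6 on Day 49: 49 − 45 = 4 > 3, so the Week 7 CO goes, although the participant attended the final visit.

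**Classification without → with footnote b.** The SAP 8.1.1 to 8.1.4 rules were applied to hypothetical participants who have complete records and are not classed as early termination. V5 is taken on Day 36 and V6 on Day 50 unless stated. CO is below 5 ppm when not smoking.

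| Participant | Primary | Sensitivity I | Sensitivity II, III |
|---|---|---|---|
| Last dose Day 30, never smokes | abstinent → non-abstinent | abstinent, no change | abstinent → non-abstinent |
| Last dose Day 45, V6 Day 49, never smokes | abstinent → non-abstinent | abstinent, no change | abstinent → non-abstinent |
| Last dose Day 30, smokes from Day 40 | non-abstinent, no change | non-abstinent → abstinent | non-abstinent, no change |
| Last dose Day 18, smokes throughout Weeks 4-7 | non-abstinent, no change | non-abstinent → abstinent | non-abstinent, no change |

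Off-drug smokers are thus normally still classed correctly in the primary analysis, and off-drug abstainers in Sensitivity I.

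There is one narrow exception in the primary analysis: last dose Day 45, V6 on Day 47 with CO below 5 ppm, smoking reported on Day 49. Since 49 − 45 = 4, that report is dropped. One missing diary is allowed, and the participant becomes abstinent.

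**Size.** Each participant moves the rate by 1/50 = 2 points. The number who stop tablets but stay in the study is not in the documents. As an assumption, take k = 0 to 5 off-drug abstainers. Starting from 25/50:

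- k = 0: 50%
- k = 1: 48%
- k = 3: 44%
- k = 5: 40%

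**Near the benchmark.** Lower limit = p − 1.645 × √(p(1−p)/50).

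- 31/50: 0.62 − 1.645 × √(0.62 × 0.38/50) = 0.62 − 0.113 = 50.7%.
- 30/50: 0.60 − 1.645 × √(0.60 × 0.40/50) = 0.60 − 0.114 = 48.6%.

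These counts were chosen because they straddle 50%. With exact limits the same step falls one participant higher: 51.4% at 32/50 and 49.4% at 31/50.

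**The case against.** The strongest reply is that the affected group may be empty. Protocol 4.6 defines only discontinuation from the study. Protocol 5.2.2 points unresolved intolerance after dose reduction towards trial discontinuation, and protocol 6.5.6 and 9.8 pair stopping the drug for pregnancy with withdrawal. Protocol 3.1 times the safety call from the last dose, so a participant who stops on Day 30 could finish on Day 37 to 39. If such people are early terminations, they are non-abstinent in all four analyses and footnote b changes nothing for them.

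That possibility stands, but the documents do not settle it. The protocol's Explanation of Terms ties early termination to the subject's end of study. Protocol 7.5 mentions ending exposure to the drug separately from withdrawal. Protocol 5.2.2 leaves trial discontinuation to judgement, and protocol 6.6.8 times the safety call from V6. Nor is a formal discontinuation needed: the Day 45 participant who attends on Day 49 is enough.

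Two further replies have weight. In the primary analysis the usual effect is downward, which is conservative for a superiority aim. In Sensitivity I the no-smoking rule is limited to the treatment period, which is undefined for someone off drug. Even so, the last bullet of SAP 8.1.2 still sets that person abstinent.

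A reader might also infer more than the documents support:

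- **That the footnote overturns the intent-to-treat analysis.** It drops evaluations, not participants. The denominator stays intact.
- **That it covers all evaluations.** The table is for efficacy, and the treatment-emergent definition in SAP 9.2 has no such cut-off.
- **That 10 points are at stake.** The drop-out figure of nearly 10% in protocol 1.1 comes from varenicline trials and does not estimate people who stop this drug and stay. Ten points would also need all five to be abstainers.
- **That the gap between the primary result and Sensitivity I merely reflects deletion.** The two also differ in how they treat missing diaries and CO in everyone still on drug.

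**Conclusion.** The point holds in limited form. As written, footnote b puts an on-treatment cut-off on outcome data for an endpoint declared intent-to-treat. For a participant who stops tablets, still attends and reports, and is not classed as early termination, observed abstinence is lost in the primary analysis and in Sensitivity II and III. In Sensitivity I, observed smoking can be erased and scored as abstinence. That second effect conflicts most directly with the rule that smoking in Weeks 4-7 is non-abstinent.

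The size is 2 points per participant, over an unknown number that may be zero. One participant can move the lower limit across 50%. That does not show that a trial decision would change: the SAP analysis is descriptive, and the thresholds mentioned in protocol 11.2 are not stated in the readable text. The conclusion assumes that excluded evaluations are handled as missing, which the SAP implies but does not say. The change should be made because it is small and stops observed outcomes being discarded.

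**What to change.** 1. In SAP 5.4, state that footnote b does not apply to the diary and CO data used in 8.1 and 8.3.6 to 8.3.8, so that all on-study records in Weeks 4-7 are used regardless of dosing. The footnote can remain for other on-treatment efficacy summaries.
2. In SAP 8.1, state whether early termination means ending the study or ending the drug. If it includes ending the drug, those participants are non-abstinent throughout and the text should say so openly.
3. In SAP 8.1, state that recorded smoking in Weeks 4-7 counts as non-abstinent in every analysis, including Sensitivity I.

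The cost is a few sentences in the SAP. The change uses records already collected while participants remain in the study. It needs no new data and adds no visits.
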